2.6 Recruitment

Patients will not be formally recruited for participation in the study. The intervention involves practice-level promotion of an existing feature of Inova's MyChart: electronic blood glucose flowsheets. Promotion of this feature does not represent a change in standard of care, and will not be formally mandated by the study design.

3. Study Methods and Procedures

3.1 Study Treatment/Intervention

The focus of the study treatment will be to encourage adoption of the blood glucose monitoring feature of MyChart by patients with diabetes and their providers. Currently, providers must place an order to allow patients to enter their blood glucose into the online system. If patients enter data, providers are then able to view these readings through the patient portal. This feature is currently available, but awareness and utilization are low. The sections describe intervention design, which will promote adoption.

3.1.1 PRACTICE LEVEL PROMOTION

Providers in the randomly selected group of treatment primary care practices will be encouraged to batch order blood glucose flowsheets for all patients with diabetes with active MyChart accounts. The research team will contact physicians and practice managers with an explanation of the initiative and instructions for completing batch orders and viewing entries through the system. The practice will be advised to complete filling orders over a two week administration period, after which the implementation period will begin. A batch order will trigger two forms of alerts sent to providers, according to the default settings for electronic glucose flowsheets:

1. A bi-weekly report received of values that the patient has entered, or a notification that the patient has not entered data during the interval.
2. A notification when patient entered values are out of range (the patient also gets a notification that their doctor will see this value) according to the following current settings:

Notification Setting	Current Default
Pre-Meal Range (entry outside range=alert)	60-180 mg/dl
Post-Meal Range	100-240 mg/dl
Nighttime Range	60-300 mg/dl

Patients will automatically be notified when the flowsheet has been ordered for them. Additionally, providers will be given text for a secure smart-text message to send to all patients receiving the flowsheets, instructing them to enter data for the study period. The secure message will also provide them with information on how to enter data, and on the benefits of tracking blood glucose. Draft text of this message is included below:

Dear [Patient],

You may have seen that there is a new electronic form available for you to enter your blood glucose results in the MyChart portal. Keeping track of your blood glucose can help you manage your diabetes and reduce your chances for developing complications like heart disease, kidney damage and eye damage. As part of a new Inova program to help patients with diabetes get healthy, I would like you to try entering the results of your home blood glucose tests on MyChart for the next 3 months, through [Date]. Please let me know if you have any questions.

Sincerely,

[Practitioner]

WHAT TO DO NEXT

1. **Get help:** If you need help learning how to measure your blood glucose or getting testing supplies, you can contact [Practice Contact].

2. **Learn how:** See [insert link to instructions/screenshots] to learn how to use the electronic blood glucose flowsheets on MyChart
3. **Link your devices:** You don't need to have special equipment to use the flowsheets, but if you have an Apple/iOS device and compatible glucometer, you can set up automatic data transfer. This will pull the results of your glucose tests into MyChart automatically, making it even easier to track. See [insert link to instructions] for help setting this up, and for a list of compatible devices.
4. **Track your blood glucose:** For the next 3 months, try to enter at least 6 measurements total per week, spread out over a few different days. However, don't be discouraged if you miss a day-- even tracking occasionally could be beneficial to your health.

Note: If you've never tested your blood glucose before, get in touch with [Practice Contact] to make sure you have all the materials and instructions you need, and to confirm that testing is right for you. Patients who think they might be pregnant should also be sure to talk to a physician before starting any new tracking regime.

3.1.2 INDIVIDUAL LEVEL REMINDERS

After the initial two-week roll-out/administration period, follow-up emails will be sent out by the research team to patients at treatment practices whose doctors have placed blood glucose flowsheet orders. Patients will be assigned at the individual level to one of four reminder treatment conditions, which will be administered by the research team. The number of reminder conditions may be reduced (to 2 or 3 instead of 4) depending on the rate of flowsheet orders by physicians to preserve statistical power. Assignment to any of these treatments will not preclude or provide guidelines for other communication between providers and patients (e.g. providers are free to send out their own reminders or messaging regardless of patient assignment to treatment group). The four reminder treatment conditions are described below:

(1) No additional reminders from research group

(2) Standard secure message reminder, addressed from Inova Medical Group, sent every two weeks during 12 week implementation period. Draft text below:

*Dear [Patient],
Don't forget to track your blood glucose through MyChart! Keeping track of your blood glucose can help you manage your diabetes and reduce your chances for developing complications like heart disease, kidney damage and eye damage.
Sincerely,
Inova Medical Group*

(3) Secure message reminder with chance to receive gift card, addressed from Inova, sent every two weeks during 12 week implementation period. Draft text below:

*Dear [Patient],
You have been chosen for a special program to help you get started tracking your blood glucose through MyChart. For each day that you track your blood glucose on MyChart through [DATE], you will be*

entered to receive one of fifty \$50 gift cards to Amazon. You'll be sent a secure message through MyChart after [DATE] if you've been selected to receive a gift card. Keeping track of your blood glucose can help you manage your diabetes and reduce your chances for developing complications like heart disease, kidney damage and eye damage.

Sincerely,

Inova Medical Group

(4) Secure message reminder, addressed from primary care doctor, sent every two weeks during 12 week implementation period. Draft text below:

Dear [Patient],

Don't forget to track your blood glucose through MyChart! Viewing your results helps me to respond if they are out of range, and improve your diabetes treatment to help you stay healthy. We will talk about your results at your next office visit. Keeping track of your blood glucose can help you manage your diabetes and reduce your chances for developing complications like heart disease, kidney damage and eye damage.

Sincerely,

[Practitioner]

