2.5 Study Population

Non-pregnant adult patients of Inova physicians at primary care sites other than Ashburn II Primary Care, Lake Ridge Primary Care and Springfield Primary Care with a current diabetes mellitus diagnosis and active MyChart account at time of treatment administration will be included in the study. There will be no gender, age, racial or ethnic exclusions of adult patients, and study population is expected to match the

distribution of diabetic patient characteristics in Inova health system. Patients will not be formally recruited for participation in the study. The intervention involves practice-level promotion of an existing feature of Inova's MyChart: electronic blood glucose flowsheets. Promotion of this feature will not be formally mandated by the study design. All communications and interactions included in the study will take place electronically through MyChart.

Physicians will exclude from initial bulk flow sheet orders any individual patients whom they identify as having contraindications for tracking of blood glucose.

[figure not shown]

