4.1 Sample Size

Non-pregnant adult patients of Inova primary care physicians with a current diabetes mellitus diagnosis and active MyChart account at time of treatment administration will be included in the study. The estimated number of patients is around 7200, from 71 primary care physicians across 24 selected Inova primary care practices.

Power Calculations

Power calculations were performed using the “clustersampsi” command in Stata. Knowledge of available sample and estimates/assumptions of control outcome mean, variance, and intraclass correlation were used to calculate a minimum detectable effect size for the key outcomes of flowsheet adoption (extensive margin, dichotomous rate of adoption) and changes in mean A1c.

Flowsheet Adoption: Practice Level Treatment-Control Comparison

Sample Size: 7200

Number of Treatment Arms: 2

Number of Clusters: 24

Assumed Control Adoption Rate: 2%

Assumed Intra-Cluster Correlation (within practices): 0.1

Minimum Detectable Effect: **9.5 percentage point increase in flowsheet orders**

Mean HbA1c: Practice Level Treatment Control Comparison

Sample Size: 7200

Number of Treatment Arms: 2

Number of Clusters: 24

Assumed Control HbA1c Mean: 6.74

Assumed Control HbA1c Standard Deviation: 1.39

Assumed Intra-Cluster Correlation (within practices): 0.07

Assumed Baseline Correlation: 0.80

ITT Minimum Detectable Effect: **0.27 change in A1c**

Flowsheet Adoption: Individual Level Comparison between Messaging Assignment Groups in Treatment Practices

Sample Size: 3600

Number of Arms (including no reminder): 4

Assumed No Reminder Adoption Rate: 20%

Minimum Detectable Effect: **5.5 percentage point increase in use of flowsheets when compared to no reminder**

Justification

The sample size represents the entire population of Inova primary care patients with diabetes who have active MyChart accounts and are therefore able to access the blood glucose tracking feature. The minimum detectable effects resulting from power calculations above are in-line with similar studies cited in the protocol background. Metastudy reviews of the effect of self monitoring of blood glucose found a 0.33 point change in A1c.

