6.2 Payment

There will be no payment for participation. A subset of participants in the treatment group--one quarter of patients with diabetes in 10 randomly selected practices--will have the chance to receive one of 50 \$50 gift card to Amazon.com if they choose to enter data into the flowsheet for any day during the study period (chance will be increasing in the number of days flowsheet is used). This gift card is intended as compensation to offset hassle costs of entering data into the flowsheet, and not as an incentive to participate in the study. Study personnel will follow guidelines from section 11.10 of IRC on the distribution of gift cards.

The code for online redemption of the gift card will be sent to selected recipients who remain MyChart activated at the time of distribution in a secure message through MyChart. The subject line will read Gift Card Recipient: MyChart Glucose Tracking Program. Patient replies will be disabled for this communication. We will track read-receipts after one month, but will not re-send messages or take any action based on this information. The message will read as follows:

We're pleased to let you know that you were selected to receive a \$50 gift card to Amazon.com! You were chosen for a special program through Inova to help you get started tracking your blood glucose through MyChart. For each day that you tracked your blood glucose on MyChart between May and August 2018, you were entered to receive one of fifty gift cards. You tracked, and one of your entries was randomly selected! To redeem your gift card, visit <https://www.amazon.com/gc/redeem> and enter [code].

7. Adverse Event Reporting

Risks from participation in this study are minimal, but one possible adverse event is breach of confidentiality. Adverse events will be reported in accordance with IRC 11.16.

8. Funding

Key Personnel [name] has received a small J-PAL North America HCDI Project Development grant (less than \$5000) to cover gift cards, and personal travel costs. The grant will be administered directly to [name] and will not pass through the Inova grant office.

9. Conflicts of Interest

None.

10. Facilities and Equipment

Data analysis will be conducted through remote access to Inova Citrix systems. The intervention will be administered primarily through MyChart, and will not require any additional equipment or facilities.

11. Outside Collaborators

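### The 5.5-point reminder MDE in Section 4.1 counts all 3,600 treatment-practice patients, although reminders go only to patients with a flowsheet order, and makes no allowance for patients not ordered

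*Combined protocol and SAP*

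**What the plan says.** Section 3.1.2 limits the reminder stage to patients with an order: "follow-up emails will be sent out by the research team to patients at treatment practices whose doctors have placed blood glucose flowsheet orders". Section 3.1 explains that the order is what opens data entry to the patient. Section 2.5 takes some patients out of the orders: "Physicians will exclude from initial bulk flow sheet orders any individual patients whom they identify as having contraindications for tracking of blood glucose". Sections 2.5 and 2.6 say that promotion of the feature is not mandated, and Section 3.4 makes the fraction of patients ordered an outcome of the trial.

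Section 4.1 gives the overall population: "The estimated number of patients is around 7200, from 71 primary care physicians across 24 selected Inova primary care practices". For the reminder comparison it lists "Sample Size: 3600", "Number of Arms (including no reminder): 4" and a no-reminder adoption rate of 20%, and states the result as "5.5 percentage point increase in use of flowsheets when compared to no reminder". It mentions no order rate.

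Two further passages matter. Section 3.1.2 allows the four conditions to be cut to three or two, depending on how many orders are placed, to protect power. Section 3.4 defines the reminder comparison across assignment groups inside treatment practices and does not require an order.

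**The concern.** The sample size behind the reminder MDE is the whole treatment half of the study. The people who can receive a reminder, and respond to it by entering data, are the subset with an order. The two counts agree only if every patient in every treatment practice is ordered. The plan provides for exclusions and leaves ordering to the physician.

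At stake is the planning figure for hypothesis 1.2.2. If the ordered group is materially smaller than 3,600, the four-condition design has less power at 5.5 points than Section 4.1 implies. The decision in Section 3.1.2 on how many conditions to run would also be taken without a figure that shows how the MDE depends on the order rate.

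**Working it through.** **Inputs.** From Section 4.1: 7,200 patients, 3,600 for the reminder comparison, four arms, 20% adoption without reminders, MDE 5.5 points. Equal arms are consistent with Section 6.2, which describes the gift-card group as "one quarter of patients with diabetes in 10 randomly selected practices". Section 4.1 does not state alpha, sidedness or power for this comparison. I assume two-sided 5%, 80% power, independent patients and no multiplicity adjustment. The order rate f is not given, so a range is shown.

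**Formula.** With p1 the no-reminder rate, p2 = p1 + d and p̄ = (p1 + p2)/2, the number per arm is

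n = [1.96·√(2p̄(1−p̄)) + 0.8416·√(p1(1−p1) + p2(1−p2))]² / d².

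The MDE is the d that solves this for the available n.

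**Step 1: reproduce the plan.** 7,200/2 = 3,600 and 3,600/4 = 900 per arm. At p1 = 0.20 the solution is d = 5.53 points, matching the stated 5.5. Other conventions at 900 per arm do not round to 5.5: one-sided 5% gives 4.89, 90% power gives 6.44, alpha of 0.05/3 gives 6.44, and a continuity correction gives 5.65. In the other direction, d = 0.055 gives p̄ = 0.2275 and n = (1.1620 + 0.4979)²/0.055² ≈ 911 per arm, or 3,644 in four arms. The stated figure therefore uses all 3,600 patients and has nothing in reserve.

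**Step 2: analyse ordered patients only.** n per arm = 3,600·f/k for k conditions, with 20% as the no-reminder rate among ordered patients.

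| Ordered | Patients | MDE, 4 conditions | MDE, 3 | MDE, 2 | Power at 5.5 points, 4 conditions |
|---|---|---|---|---|---|
| 100% | 3,600 | 5.53 | 4.76 | 3.86 | 79.5% |
| 90% | 3,240 | 5.85 | 5.03 | 4.08 | 75% |
| 75% | 2,700 | 6.43 | 5.53 | 4.48 | 67% |
| 50% | 1,800 | 7.96 | 6.84 | 5.53 | 50% |
| 25% | 900 | 11.52 | 9.88 | 7.96 | 28% |

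Three conditions keep about 5.5 points down to roughly 75% ordered, and two down to roughly 50%. Below that, no reduction that Section 3.1.2 permits restores 5.5.

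**Step 3: vary the base rate.** Selective ordering could move adoption among ordered patients away from 20%. At 50% ordered (450 per arm) the four-arm MDE is 6.3 points at a 10% base, 8.0 at 20% and 8.9 at 30%.

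**Step 4: analyse all 3,600 by assignment group.** N stays at 900 per arm, but patients without an order cannot adopt, so an effect among ordered patients is diluted by f. At f = 0.5:
- If 20% is the rate among ordered patients, the overall rate is 0.20 × 0.5 = 10%. The MDE over all patients is 4.31 points, which needs 4.31/0.5 = 8.6 points among ordered patients.
- If 20% is the overall rate, the ordered patients' rate is 0.20/0.5 = 40%. The MDE over all patients stays at 5.53, which needs 5.53/0.5 = 11.1 points among ordered patients.

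**The case against.** A reader might infer that 5.5 points can be had only if every patient is ordered. The documents do not support that. Section 3.4 compares assignment groups inside treatment practices without conditioning on an order, and Section 3.3 assigns by last name, which every patient has. On that reading 3,600 is the right N at any order rate, and the MDE over all patients can even be below 5.5 (4.31 in Step 4). This stands, and it makes the population ambiguous. It does not rescue the figure as a statement about patients who can respond to a reminder: the effect needed among them still rises as the order rate falls.

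A reader might also take the remark in Section 1.3 that orders are seldom placed as a forecast of low ordering. It describes practice before the intervention, which is meant to remove that barrier through batch orders. Ordering could be close to complete, and at 90% the loss is small (5.85 against 5.53). The size of the exclusions in Section 2.5 is not stated either.

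Section 3.1.2 already recognises that power depends on orders. That is a fair defence of the design, but the section gives no MDE at any order rate below 100%.

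The documents' counts also differ. Section 2.4 estimates 9,000 patients, half of them treated. Against 4,500, a count of 3,600 would be 80% ordered. But Section 4.1 derives its power from 7,200, and half of that is exactly 3,600, so an order-rate allowance is not the natural explanation. Section 6.2 points the other way: it refers to 10 treatment practices, and at 7,200/24 = 300 patients each that is 3,000 patients and an MDE near 6.1 even with everyone ordered.

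Finally, it would be too strong to say that a null result would be taken to exclude 5.5 points. The achieved confidence interval decides that, not the planning MDE.

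**Conclusion.** The point holds in this form: the stated 5.5-point MDE for the four-condition reminder comparison rests on every treatment-practice patient and makes no allowance for patients without an order, who receive no reminder and cannot adopt. If only ordered patients are analysed, the MDE is 5.9, 6.4, 8.0 and 11.5 points at 90, 75, 50 and 25% ordered. If all 3,600 are analysed, the corresponding problem is dilution: 8.6 or about 11 points needed among ordered patients at 50% ordered.

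The direction is certain if any patient goes without an order and the base rate among those analysed is 20%. The size depends on an order rate that the documents do not give. The figures further assume a two-sided 5% test, 80% power, equal arms and independent patients. The point is worth correcting, but it does not show that the reminder comparison is unworkable.

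**What to change.** In Section 4.1, state which population the reminder comparison uses: treatment-practice patients with an order when reminders start, or all treatment-practice patients by assignment group. Reconcile Sections 3.1.2 and 3.4 accordingly, and say whether the 20% refers to ordered or to all patients. State alpha, sidedness and power.

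Replace the single N of 3,600 and MDE of 5.5 with a short table of MDE by order rate for four, three and two conditions, as in Step 2, with the base-rate assumption shown. If all patients are analysed, add the effect needed among ordered patients.

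Use the table to inform the existing option in Section 3.1.2 to run fewer conditions: three keep about 5.5 points down to roughly 75% ordered, two down to roughly 50%. These values should serve as guidance and not as mandatory cut-offs. Read strictly, a 5.5-point rule would bar four conditions even at 100% ordered, since 3,644 patients are needed, and how many conditions to keep is a design trade-off for the sponsor.

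The cost is some wording, one table and a less favourable stated MDE. No extra patients are needed and the intervention does not change.

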3.2 Control Group

The control group will be randomly selected half of the 27 primary care practices, and will receive no encouragement of adoption. However, this group will not be explicitly discouraged from making flowsheet orders.

3.3 Randomization

Provider-side treatments will be cluster randomized at the practice level. Randomization will stratify across practices by number of diabetic patients (cluster size), and will be conducted using a random number generator at the outset of the study. Reminder messaging treatments will be assigned alphabetically by first two letters of patient last name, as it is logistically infeasible to do individual level patient messaging without sorting on an existing field in the patient's EHR. There are some concerns that ethnicity could correlate with assignment based on last name spelling, so this form of assignment is "pseudo-random". However, the patient's race/ethnicity recorded in the medical record will be controlled for in the analysis. Causal interpretation of the results of the reminder messaging portion of the experiment will thus require the assumption that grouped last name spelling is not independently related to likelihood of flowsheet adoption.

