4.2 Method of Data Analysis

All data analyzed in this study will be administrative health and use data that is collected as part of routine medical care and record keeping. EPIC has offered to build the SQL queries required to produce the outcome datasets described in this protocol. Outcomes listed in Section 3.4. will be analyzed using regression analysis, including (a) a version with no covariates, (b) a version controlling for patient age/gender, race/ethnicity, A1c at baseline, days since most recent office visit at baseline, and doctor fixed effects. A flag identifying patients who are eventual participants of "Impact of Innovative Interventions on Diabetic Adherence with Digital Sensors" (a study recently submitted to the IRB that may have limited overlap with this population) will also be included in the controls. For outcomes indicating analysis of practice level treatment and control groups, standard errors will be clustered at the practice level.

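### Practices are randomised within size strata, but the no-covariate model omits the strata; this costs precision, not validity, if practice size predicts the outcome

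*Combined protocol and SAP*

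**What the plan says.** Section 3.3 makes the practice the unit of allocation: "Provider-side treatments will be cluster randomized at the practice level". It then restricts that allocation: "Randomization will stratify across practices by number of diabetic patients (cluster size". It gives neither the number of strata nor the cut-points.

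Section 4.2 gives two regressions for the outcomes in section 3.4. The first is "a) a version with no covariates". The second is "b) a version controlling for patient age/gender, race/ethnicity, A1c at baseline, days since most recent office visit at baseline" "and doctor fixed effects", plus a flag for participation in another study. For practice-level comparisons, "standard errors will be clustered at the practice level". Neither list contains the size strata or practice size, and no small-sample correction is mentioned.

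The power calculations in section 4.1 (Sample Size) do not mention stratification.

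**The concern.** Stratified allocation balances the arms on practice size, so size-related differences between practices drop out of the treatment contrast. If the model leaves the strata out, those differences stay in the residual. The standard error then estimates a larger variance than the contrast has, tests become conservative and power is lost. The treatment estimate itself is not biased, provided about half the practices in each stratum are treated.

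With 24 practices, between-practice variance governs precision for every practice-level comparison in section 3.4, so some power is at stake. How much depends on whether practice size predicts the outcome.

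**Working it through.** **Inputs from section 4.1.** 7200 patients, 24 practices, 71 physicians; A1c SD 1.39, intra-cluster correlation (ICC) 0.07, baseline correlation 0.80, minimum detectable effect (MDE) 0.27.

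**Assumptions.** 12 practices per arm, averaging 300 patients; two-sided 5% significance and 80% power (not stated, but they reproduce the plan's figure); three strata of 8 practices, 4 treated in each; R² is the share of between-practice variance explained by the strata. R² is not in the documents, so a range is shown.

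**Step 1: reproduce the plan's MDE.**

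- Baseline-adjusted SD = 1.39 × √(1 − 0.80²) = 0.834.
- Design effect = 1 + 299 × 0.07 = 21.93.
- MDE = (t₂₂,₀.₉₇₅ + t₂₂,₀.₈₀) × 0.834 × √(2 × 21.93 / 3600) = (2.074 + 0.858) × 0.834 × 0.1104 = 0.270, as stated.

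Version (a) does not adjust for baseline A1c. With SD 1.39 its MDE is 2.932 × 1.39 × 0.1104 = 0.45.

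**Step 2: MDE with strata in the model.** Multiply by √{[(1 − R²) × 0.07 + 0.93/300] / [0.07 + 0.93/300]} and by the ratio of t-multipliers on 20 and 22 degrees of freedom, (2.086 + 0.860)/(2.074 + 0.858) = 1.005. At R² = 0.25 this is √(0.0556/0.0731) × 1.005 = 0.872 × 1.005 = 0.876.

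| R² | MDE, baseline-adjusted | MDE, version (a) plus strata |
|---|---|---|
| 0 (strata included, no gain) | 0.271 | 0.45 |
| 0.10 | 0.258 | 0.43 |
| 0.25 | 0.237 | 0.39 |
| 0.50 | 0.196 | 0.33 |

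**Step 3: simulated power and type I error, equal practices, cluster-mean analysis.** SD 0.834, ICC 0.07, t-test on 22 degrees of freedom without strata and 20 with.

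| R² | Type I error without strata | Power at 0.27 without strata | Power at 0.27 with strata |
|---|---|---|---|
| 0 | about 5% | 80% | 80% |
| 0.20 | about 3% | 81% | 87% |
| 0.40 | about 1% | 84% | 94–95% |

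With strata in the model, type I error stays at about 5% throughout.

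**Step 4: closer to the planned analysis.** Strata defined by size imply unequal practices. Take practices of 100, 300 and 500 patients (assumed), regression weighted by patients, cluster-robust errors with only the usual G/(G − 1) factor, and a t reference on 23 degrees of freedom. Without strata, the mean reported SE divided by the true SD of the estimate was:

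| R² | SE ratio without strata | Type I error without strata |
|---|---|---|
| 0 | 0.92 | about 7% |
| 0.10 | 0.95–0.98 | 6–7% |
| 0.20 | 1.00–1.01 | 5.2% |
| 0.25 | 1.03 | 4.7% |
| 0.40 | 1.09 | 3.8% |
| 0.50 | 1.17 | 2.4% |

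The reported SE is therefore too small below a share of about 20%, about right there, and too large above it. In the same setting, adding strata with no small-sample correction gave type I error of roughly 7–9%, so part of the apparent power gain would be liberal testing.

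**Step 5: version (b).** If each of the 71 doctors belongs to one practice (an assumption), any practice-level variable is a sum of doctor indicators. A design matrix of 71 doctor indicators has rank 71, and still 71 after adding treatment and strata. The strata are already absorbed, and so is the practice-level treatment.

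**The case against.** The strongest objection is that the documents give no evidence that practice size predicts A1c, contact, medication changes or adoption. At a zero share nothing is lost. The share in the A1c figures must also be size-related variance left after adjustment for baseline A1c, which is a demanding assumption. This stands: the loss is conditional, only A1c was worked through, and its size cannot be fixed from the documents.

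A second objection is that the power figures in step 3 belong to neither planned model. They need the baseline-adjusted SD, which version (a) does not use, and a treatment effect that can be estimated, which version (b) does not give if doctors are nested in practices. This also stands. The figures describe a baseline-adjusted model without doctor fixed effects. Version (a) as written has an MDE of about 0.45, hence power of roughly 40% at 0.27.

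A reader might infer that the planned practice-level standard errors are simply too large. The documents do not support that: step 4 shows that the direction depends on the share and on how unequal the practices are. Nor do two offsetting errors make the analysis sound, because the offset is accidental.

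A reader might also infer that version (b) leaves the strata in the residual. It does not, if each doctor has one practice. That it cannot then estimate the practice-level effect is a separate and more serious fault, and should not be counted as weight for this one.

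**Conclusion.** The point holds as a conditional loss of precision. The allocation is stratified by practice size, and version (a), the only listed model that can estimate a practice-level effect if doctors are nested in practices, ignores the strata. The estimate is not biased by this if allocation is balanced within strata.

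Under the assumptions of step 3 the cost at an A1c difference of 0.27 is nil at a 0% share, about 6 power points at 20% (81% v 87%) and about 10 at 40% (84% v 94–95%). These figures rest on an assumed number of strata, equal practices and an assumed share, none of which the documents give. Whether reported standard errors would be too wide is not settled: with unequal practices and uncorrected cluster-robust errors they may be too narrow up to a share of about 20%. The change is worth making because it costs little and matches the analysis to the randomisation, but only together with a small-sample correction or a randomisation test.

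**What to change.** In section 4.2, include size-stratum indicators in every practice-level treatment-control model: in version (a), and in a version of (b) that drops the doctor fixed effects. Adding strata to (b) while it keeps those effects would change nothing.

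In the same paragraph, specify the inference. Suitable choices are cluster-robust errors with the CR2 correction and Satterthwaite degrees of freedom, a cluster-level t-test with degrees of freedom reduced for the strata, or a randomisation test that permutes practices within the size strata. State the number of strata and the cut-points in section 3.3.

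The cost is a short edit, one degree of freedom per extra stratum (two for three strata), and slightly wider standard errors from the correction. No new data are needed, because the strata are fixed at randomisation. If size proves unrelated to outcome, the A1c MDE moves only from 0.270 to 0.271 under three strata, before any further widening from the correction.
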